8.2 ANALYSIS SETS

The primary analysis for effectiveness and safety will be based on a modified intent-to-treat principle. The per-protocol analysis set is designated as supportive.

Intent-to-Treat (ITT): the ITT set will be comprised of all subjects who have signed informed consent, meet all the inclusion and none of the exclusion criteria.

Modified Intent-to-Treat (mITT): the mITT set will be comprised of all ITT subjects who have the investigational device attempted.

Per-Protocol (PP): the PP set will be comprised of all subjects in the mITT set who have no major protocol deviations. All major protocol deviations will be reviewed and finalized before the data lock for final analysis.

8.3 STATISTICAL ANALYSIS

General Statistical Consideration

All statistical analyses will be performed using Statistical Analysis System (SAS) for Windows (version 9.1 or higher, SAS Institute Inc. Cary, NC) or other widely accepted statistical or graphical software. It is planned that the data from all sites that participate in this protocol will be combined for analysis.

Descriptive statistics will be used to present the data and to summarize the results. Discrete variables will be presented using frequency distributions and cross tabulations. Continuous variables will be summarized by presenting the number of observations (N), mean, standard deviation, median, minimum, and maximum values. Unless otherwise specified, the analyses will be performed using descriptive statistics.

A statistical analysis plan (SAP) accompanies this protocol and should be referred to for further information on intended statistical methods; the SAP will be finalized and approved prior to study database lock. The SAP will detail the analytical methodology and assumptions beyond those presented below.

Anaysis of Primary Endpoints

The study will be considered a success if both primary effectiveness and safety objectives are met using the mITT Set at the one-sided 0.025 level of significance in the final analysis.

Analysis of Primary Safety Endpoint

The analysis of primary safety endpoint (i.e., freedom from MAE at 30 days) will be performed in the mITT analysis set. The primary safey will be assessed by calculating the proportion of subjects who have no MAE at 30 days aggregated over the mITT subjects. A 95% two-sided confidence interval will be estimated using the Clopper-Pearson interval (F-distribution method).

In case of missing data that is of concern at 30 days when the primary safety endpoint is evaluated, the probability of a subject achieving freedom from MAE at 30 days will be estimated using Kaplan-Meier method. The standard error will be approximated using Greenwood's formula. A two-sided 95% log-log confidence interval for the probability will be constructed. The Kaplan-Meier estimate and its 95% log-log confidence interval will be constructed from the day of index procedure through the 30 days follow-up. For subjects with MAE, days of follow-up will be computed as the days from the index procedure to the onset date of the first event. For subjects without MAE, days of follow-up will be computed as the days from the index procedure to the last follow-up at the time of data lock for primary analysis.

If the lower bound of this 95% confidence interval is greater than the performance goal 85%, we can conclude that the primary safety endpoint is met.

As a sensitivity analysis, a tipping-point analysis will be conducted. A tipping point is defined as the number of events in the missing cohort at which the study conclusion is changed. Let n_m be the number of missing values in the mITT cohort. Starting at 0 and ending at n_m , the event rate is changed by adding 1 event at a time. The 95% confidence interval will be calculated each time when adding 1 event.

The primary safety analysis will also be performed in the PP set as supportive evidence.

Analysis of Primary Effectiveness Endpoint

The primary effectiveness will be assessed by calculating the proportion of subjects who have achieved technical success over the mITT subjects. A 95% two-sided confidence interval will be estimated using the Clopper-Pearson interval (F-distribution method). If the lower bound of this 95% confidence interval is greater than the performance goal 86%, we can conclude the primary effectiveness endpoint is met.

The primary effectiveness analysis will also be performed in the PP set as supportive evidence.

Analysis of Secondary Endpoints

The secondary endpoints will be analyzed with descriptive statistics; there will be no formal statistical hypothesis test. Details of these statistical analyses will be provided in a separate standalone Statistical Analysis Plan.

Poolability of Investigational Sites

This study is designed and conducted as a multicenter clinical trial. Data from all the sites will be pooled. All subjects will be treated and evaluated following the same protocol to ensure generalizability of the study results.

A Chi-Square test will be conducted to investigate the overall homogeneity across all sites for the primary safety and effectiveness endpoints. The tests will be conducted at the two-sided 0.15 level of significance. If the p-value is less than 0.15 then further evaluation is warranted. In addition, a graphical display of the proportions of primary safety and effectiveness success along with 95% confidence intervals for each site will be constructed. The confidence intervals will be constructed using the Clopper-Pearson interval (F-distribution method) and be plotted relative to the performance goal. Sites with fewer than 5 subjects will be first combined into an adjacent single super-site that shares similar site characteristics for these analyses. The site characteristics will be determined before data lock for statistical analysis. Two sets of poolability analyses will be conducted, one is to use all sites without any combination, the other is to combine small sites into a super-site which has similar characteristics. If the sites are not poolable, we will conduct a random effect model to determine its effect on the primary endpoints.

In addition to the homogeneity test for the primary endpoint, other variables such as baseline demographics and lesion characteristics will also be compared across sites to assess the appropriateness of pooling data from across all sites.

Analysis of Adverse Events (AE)

For AE reporting, the primary analysis will be based on subject counts. A subject with more than one event will be counted only once toward the event rate based on the total number of subjects with AEs. An event count will also be presented. For example, if a subject experiences one major unplanned amputation of the treated limb and two clinically-driven TLRs within 30 days, the subject will be counted once in the rate of total subjects with a 30-day MAE; the same subject will be counted once in the individual event category of "Major Unplanned Amputation of the Treated Limb" and twice in the "Clinically-Driven TLR" category.

9 DATA MANAGEMENT

9.1 SUBJECT IDENTIFICATION

Subjects that successfully pass the screening tests and wish to participate in the study will be assigned a unique identification code (ID) using the format "XX-YYY" where:

XX = Institution Number, assigned by the Sponsor to each study site

YYY = Enrollment Number, assigned by the institution as each subject is enrolled

in the study

⁰¹⁰⁻⁰⁵⁵ Protocol Version F

In addition to the ID, each subject's initials will be used as an identifier included on documentation submitted to the Sponsor.

9.2 CENTRAL DATABASE

All study documentation will be collected and compiled in a central database. Appropriate quality control measures will be established to ensure accurate and complete transfer of information from the study documentation to the central database.

9.3 SOURCE DOCUMENTS

Case Report Forms (CRFs) are not considered acceptable source documents. Source documents are original records in which raw data are first recorded. These may include hospital/clinic/general practitioner records, charts, for example. Source documents should be kept in a secure, limited access area. Sponsor may request copies of de-identified source document to adjudicate adverse events.

9.4 DATA COLLECTION

Data will be collected on electronic CRFs supplied by the Sponsor or designee. The principal investigator is responsible for the prompt reporting and accuracy and completeness of all study documentation. The study data are entered into the eCRFs. Corrections made after the Investigator's review and approval must be reapproved by the Investigator.

A unique study number will be assigned to each subject. All information recorded on the CRF about the subject will be recorded with the study number on it. The main database will contain only the study number to identify the subject. The code with subject name and study number will be maintained in a secured location.

9.5 DATA PROCESSING

Data will be entered / loaded in a validated electronic database using a clinical data management system. Visual and computer error checks will be carried out. The Investigator or site research personnel will be queried on errors concerning completeness and consistency. An electronic audit trail system will be maintained with the clinical data management system to track all data changes in the database once the date has been entered/loaded. Regular backups of the electronic data will be performed.

9.6 STUDY REPORT

A 30-day primary endpoint report summarizing all relevant observations will be prepared following receipt of all monitored subject data forms. The 30-day primary endpoint report will be submitted to FDA in support of 510(k) clearance.

Subjects will continue to be followed for 6 months and a final report will be prepared following study completion.

10 STUDY ADMINISTRATION

10.1 MONITORING

10.1.1 Monitoring Procedures

It is the responsibility of the study sponsor to ensure that proper monitoring of this investigation is conducted. Appropriately trained monitors, appointed by the study sponsor, will complete any monitoring that is done. The monitors will ensure that the investigation is conducted in accordance with:

- The signed Investigator's Agreement
- The Investigational Plan
- Appropriate laws and regulations
- Any conditions of approval imposed by the reviewing IRB and/or other regulatory agencies

The clinical study will be monitored according to the guidelines summarized below. The sponsor may choose to perform random inspections throughout the study as an element of quality assurance. Investigators shall allow auditing of their clinical investigation procedures.

A study specific monitoring plan standardizes monitoring activities across centers to ensure human subject protection and verify data integrity. The monitors shall receive study specific and protocol training prior to conducting any monitoring visits. Study monitors are selected based on their training, qualifications and experience to monitor the progress of an investigation. This study monitoring will include a site qualification, study initiation, interim, and close out visits. All study monitors will be required to follow the study monitoring plan and monitoring standard operating procedures.

The study monitoring will be done by the following Sponsor representative:

Libra Medical Inc.

⁰¹⁰⁻⁰⁵⁵ Protocol Version F

10.1.2 Monitoring Visit

The following factors will be taken into account when determining the frequency of the monitoring visits: subject accrual rate at each center, total number of subjects enrolled at each center, and Clinical Investigation Plan compliance at each center. It is anticipated each site will be monitored at least once upon the completion of the 30-day follow-up visits for all enrolled subjects at the study site. Monitors will require direct access to subjects' medical records pertinent to the study (and study inclusion criteria), study management documents, regulatory documents and Subject Informed Consent documents, as well as other potential applicable records not listed here.

Monitors may ensure the clinical investigators have and continue to have staff and facilities to conduct the clinical investigation safely and effectively. Monitors may conduct the following monitoring activities throughout the study:

- Verification that the current IRB-approved informed consent was signed and dated by each subject prior to participating in the study required procedures.
- Verification of documentation in the subject's record that informed consent was signed prior to initiation of the study procedures and that a copy of the signed and dated consent was provided to the subject.
- Source documentation verification by reviewing the CRFs against source documentation for accuracy and completeness of information.
- Verification that the investigation is conducted according to the Clinical Investigation Plan, Instructions for Use and, all malfunctions/ IFU deficiencies are reported as required.
- Verification that subjects met study enrollment criteria.
- Verification that study deviations are documented and reported.
- Verification that the procedures for recording and reporting adverse events to the sponsor are followed.
- Ensuring proper error correction.
- Verification of training documentation of all study personnel participating in study related activities.
- Reviewing all correspondence and regulatory documents, including confirmation of IRB-approved Clinical Investigation Plan or amendments.
- Resolution of outstanding issues and completion of assigned tasks will be documented by the monitors.

Each monitoring visit will be documented via a monitoring report and follow-up letter. The follow-up letter shall be sent to the Investigator to document issues identified, corrective actions and if applicable preventative actions. At subsequent visits any issues resolved shall be documented in this letter to demonstrate resolution.

⁰¹⁰⁻⁰⁵⁵ Protocol Version F

10.1.3 Study Closure

Study closure is defined as a specific date that is determined by study completion and/or regulatory requirements have been satisfied per the Clinical Investigation Plan (CIP) and/or by decision of the Sponsor or FDA. Study closure visits will be conducted at all enrolling clinical sites in order to review record retention requirements with site personnel. A telephone contact may take the place of a study closure visit if appropriate (e.g., low subject enrollment, recent monitoring visit, etc.) Study closure visits will be conducted by trained monitors or designees.

10.2 DEVICE ACCOUNTABILITY

Access to investigational devices shall be controlled and used only in the clinical investigation and according to the Protocol. Each site will be responsible for tracking the receipt and disposition of all investigational devices. All unused devices must be returned to the Sponsor at the end of the study.

The principal investigator or an authorized designee shall keep records documenting the receipt, use, return, and disposal of the investigational device, which shall include:

- The date of receipt
- Identification of each investigational device (serial or lot number)
- The date or dates of use
- Subject identification
- Date of return of unused, expired, or malfunctioning investigational device, if applicable
- The Investigator must explain in writing the reasons for any discrepancy noted in device accountability.

11 DEFINITION OF ADVERSE EVENT(S)

For purposes of this study, an adverse event (AE) is defined as any adverse change (i.e., de novo or pre-existing condition) from the subject's baseline medical condition(s) occurring during the course of the study. Adverse events (AE) are any untoward medical occurrence, unintended disease or injury, or untoward clinical signs (including abnormal laboratory findings) in subjects, whether or not related to the investigational medical device. For the purpose of AE documentation, the start of the course of the study is defined as any time after the treatment has been initiated. All AE's will be recorded in the CRF whether considered procedure-related or not, and will be classified as described in this section.

Pre-existing conditions will not be reported as an AE unless there is an adverse change in that condition. Any AE which resolved and then recurred will be reported as a separate AE.

An AE may be volunteered spontaneously by the subject or discovered as a result of questioning or physical examination by an investigator or study staff.

Elective procedures for a pre-existing condition (that has not worsened) are not considered AEs. Non-cardiovascular abnormal laboratory values will not be considered AEs unless:

- 1) The PI determines that the value is clinically significant,
- 2) The abnormal laboratory value required intervention, or
- 3) The abnormal laboratory value required subject termination from the trial.

All adverse events, regardless of relationship to the device, must be recorded, as applicable, on the case report forms provided. Adverse events that occur during this study should be treated by established standards of care, to protect the life and safety of the subjects.

Adverse events shall be assessed and documented at the time of the procedure and at all study follow-up visits. Each investigator shall provide source documentation as requested by the Sponsor to facilitate reporting and adjudication of these events.

11.1 SERIOUS ADVERSE EVENTS

An adverse event is considered a Serious Adverse Event (SAE) that:

- a) led to death
- b) led to a serious deterioration in the health of the subject, that either resulted in
 - 1) a life-threatening illness or injury, or

2) a permanent impairment of a body structure or a body function, or

3) in-patient hospitalization or prolongation of existing hospitalization, or

4) a medical or surgical intervention to prevent permanent life-threatening illness or injury or permanent impairment to body structure or a body function.

11.2 DEVICE RELATIONSHIP

Determination whether there is a reasonable possibility that a study product or device caused or contributed to an AE is to be determined by the Investigator and recorded on the appropriate CRF form. Determination should be based on assessment of temporal relationships, biologic plausibility, association (or lack of association) with underlying disease and presence (or absence) of a more likely cause.

11.3 UNANTICIPATED ADVERSE DEVICE EFFECT

An unanticipated adverse device effect (UADE) is any serious adverse effect on the health or safety of a subject, any life-threatening problem or death caused by, or associated with a device, if such effect, problem, or death was not previously identified in nature, severity, or degree of

⁰¹⁰⁻⁰⁵⁵ Protocol Version F

incidence in the investigational plan (e.g., ICF, Study Protocol, Instructions for Use (IFU), publications, etc.), or any other unanticipated serious problem associated with a device that relates to the rights, safety, or welfare of subjects.

If an unanticipated adverse effect associated with the investigational device occurs, the investigator shall notify the Sponsor and the IRB/EC as soon as possible.

The Sponsor will investigate the event and notify the FDA and all other participating IRBs and investigators. Should the Sponsor determine that an unanticipated adverse effect presents an unreasonable risk to all participating subjects, the Sponsor will suspend the clinical investigation and notify all participating investigators, IRBs/EC, country regulatory bodies and FDA.

11.4 ADVERSE EVENT REPORTING

The signs, symptoms and sequelae of an underlying AE should not be reported as separate AEs. All AEs must be recorded on a CRF. All AEs also must be described by (a) duration (start and resolution dates); (b) adjudicated for severity; (c) relationship to the study device; (d) action taken to resolve the event; (e) outcome of the event; and (f) whether or not such event is considered to be serious. Additional information, such as procedural notes, treatment notes, or a signed clinical summary, may be required as supporting documentation for the reported AE.

Pre-existing medical conditions or symptoms occurring prior to the start of the atherectomy procedure should not be reported as adverse events. In the situation where there is a worsening of a pre-existing medical condition or symptom due to a study related procedure, an adverse event should be reported.

For any adverse event that is ongoing at the time of the initial report, periodic follow-up information is required until the adverse event is resolved or is judged to be chronically stable. The site should submit relevant follow-up information related to the adverse event as soon as it is available.

Depending upon the nature and seriousness of the adverse event, the sponsor or designee may request the Investigator to provide copies of the subject's medical records (such as the subject's laboratory tests and hospital records, Investigator summaries, etc.) to document the adverse event.

The Investigator will report all serious adverse events, including unanticipated adverse device effects, to the IRB according to the IRB requirements. A copy of this IRB communication should be sent to the Sponsor. In case of an unanticipated adverse device effect occurred, the investigator must report to the Sponsor within 10 working days of the site first becoming aware of the event.

Within 10 working days of notification, the Sponsor will report all unanticipated adverse device effects to the appropriate authority, all participating investigators, and all reviewing IRBs. The Sponsor will ensure that safety reporting for the study is conducted in compliance with all pertinent requirements and regulations.

⁰¹⁰⁻⁰⁵⁵ Protocol Version F

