5.2 PRIMARY SAFETY ENDPOINT

The primary safety endpoint is freedom from a composite of new onset major adverse events (MAE) through 30-day follow-up as adjudicated by an independent clinical events committee (CEC).

The components of the MAE are defined as:

- 1. Cardiovascular related death: All cardiovascular cause mortality.
- 2. **Myocardial infarction (MI):** Any newly diagnosed MI post procedure, defined as CK-MB ≥2X upper limit normal (ULN).
- 3. Clinically driven target lesion revascularization (TLR): any repeat percutaneous or surgical intervention to treat objectively documented symptoms of recurrent ischemia attributable to the treated lesion.
- 4. **Clinically significant target vessel dissection:** NHLBI grade C or greater as confirmed by angiography.
- 5. Clinically significant target vessel perforation: NHLBI Type III as confirmed by angiography.
- 6. **Unplanned major target limb amputation:** Amputation of the transmetatarsals or higher that was not previously planned as part of the overall treatment strategy.

- 7. **Clinically relevant distal embolization:** Emboli requiring surgical or medical intervention and/or the presence of symptoms.
- 8. **Pseudoaneurysm:** disruption/weakening of the arterial wall at the treatment site as confirmed by angiography.

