12.2 CLINICAL EVENT COMMITTEE

The Clinical Events Committee (CEC) is an independent adjudication body comprised of qualified physicians who are not participants in the trial. An independent CEC will be utilized for this study. The CEC will be responsible for adjudicating the seriousness and relatedness of all endpoint events and serious device and/or procedure related adverse events occurring during the study period. The CEC will meet regularly. All available data (including lab reports, films, discharge reports, etc.) will be available to adjudicate the events. The committee will also review and rule on all deaths that occur throughout the trial. The composition, guiding policies, and operating procedures governing the CEC are described in a separate CEC Manual of Operations.

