## 6.3.6 Rate of Clinically-Driven Target Lesion Revascularization

Rate of clinically-driven target lesion revascularization (TLR) at 30 days and 6 months.

Clinically-driven TLR will be adjudicated by the CEC. The date of the clinically-driven TLR will be determined from the revascularization date reported on the site-reported form corresponding to the site-reported adverse event that the CEC adjudicated as a clinically-driven TLR.

Clinically-driven TLR will be analyzed on a *per-subject* basis. For subjects with more than one lesions, if at least one of the lesions has a clinically-driven TLR, the subject will fail the endpoint. The date of the earliest clinically-driven TLR will be used as the basis of determining a failure for time to event analysis in Section 6.1.5. The rates at 30 days and 6 months will be estimated for the mITT set from a Kaplan-Meier analysis.

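### Protocol 11.4 can be read as calling for an adverse event report of worsening pre-existing disease only when a study procedure caused it, which contradicts section 11 and can understate the AE tables

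*Protocol*

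**What the plan says.** Protocol section 11 defines an adverse event as "any adverse change (i.e., de novo or pre-existing condition) from the subject's baseline medical condition(s) occurring during the course of the study". It adds "All AE's will be recorded in the CRF whether considered procedure-related or not", and on existing disease it says "Pre-existing conditions will not be reported as an AE unless there is an adverse change in that condition". None of these statements carries a causality condition.

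Protocol 11.4, the section on reporting, opens its paragraph on existing disease with a prohibition: "Pre-existing medical conditions or symptoms occurring prior to the start of the atherectomy procedure should not be reported as adverse events". The next sentence names one situation in which an AE should be filed: "In the situation where there is a worsening of a pre-existing medical condition or symptom due to a study related procedure".

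Protocol 12.2 makes the Clinical Events Committee (CEC) responsible for "adjudicating the seriousness and relatedness of all endpoint events and serious device and/or procedure related adverse events occurring during the study period". SAP 6.3.6 takes the date of a clinically driven target lesion revascularisation (TLR) from the site form that corresponds to the "site-reported adverse event that the CEC adjudicated as a clinically-driven TLR". SAP 6.3.7 uses the same link for target vessel revascularisation (TVR).

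**The concern.** Two sections of one protocol give a site different instructions for the same event. The difference matters because of who is enrolled. Inclusion criterion 4 requires Rutherford class 2 to 5, so claudication, rest pain or ischaemic wounds are pre-existing in every subject. Later deterioration of the treated limb is then, by construction, worsening of a pre-existing condition. An investigator who regards it as natural progression could follow 11.4 and file nothing.

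The direct stake is the AE tables and listing, which are built from filed AEs. The indirect stake is the route by which a TLR, TVR or unplanned major amputation becomes known to the CEC. The trial has one arm and a fixed performance goal, and the treating investigator judges cause. Any loss of MAEs would therefore push freedom from MAE upward.

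**Working it through.** The plan gives no figure on this point, so the main check is a comparison of texts.

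**Step 1. Apply both sections to the same cases.**

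| Case after treatment starts | Section 11 | Section 11.4 |
|---|---|---|
| Pre-existing condition, unchanged | Not an AE | Not an AE |
| New condition | AE | AE |
| Pre-existing condition, worse, due to a study procedure | AE | AE |
| Pre-existing condition, worse, not due to a study procedure | AE | Not named; falls under the prohibition if the stated exception is the only one |

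The conflict is confined to the last row. Section 11 answers that row plainly. Section 11.4 does not, and its most natural reading gives the opposite answer.

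**Step 2. Effect on the AE tables.** SAP 6.4 counts subjects and events from AEs and lists them by subject. It names no other source. Scheduled Rutherford class, ABI/TBI and duplex at 30 days and 6 months would record some of the same worsening, and SAP 6.3.3 and 6.3.4 report worsened categories for ABI and Rutherford. A subject could therefore appear as worsened in the secondary tables with no matching AE. Nothing in either document sends those findings to the AE form or to the CEC. Protocol 6.9 asks for an AE after an unscheduled visit for new symptoms only where applicable, so it does not settle the matter.

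**Step 3. Route to the MAE composite.** Worsening ischaemia is not itself an MAE. It enters the composite mainly through two of the eight components: unplanned major amputation of the target limb, and clinically driven TLR, defined as "any repeat percutaneous or surgical intervention to treat objectively documented symptoms of recurrent ischemia attributable to the treated lesion". The CEC remit covers all endpoint events, but no passage says how the CEC learns of one for which the site filed no AE. SAP 6.3.6 and 6.3.7 describe only the path through a site-reported AE.

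**Step 4. Context from the safety test.** The exact two-sided 95% lower bound for x event-free subjects out of n is the 0.025 quantile of Beta(x, n − x + 1), compared with the 85% goal.

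| n | MAEs | x | Lower bound | Result |
|---|---|---|---|---|
| 102 | 8 | 94 | 85.13% | met |
| 102 | 9 | 93 | 83.91% | not met |
| 112 | 9 | 103 | 85.29% | met |
| 112 | 10 | 102 | 84.19% | not met |

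At n = 102 and a true rate of 95%, the limit of 8 MAEs gives 93.0% power, which agrees with the plan's claim of at least 90%. For the 6-month TLR rate, one missed event in 112 subjects is 1/112 = 0.9 percentage points, ignoring censoring.

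These figures show how sensitive the analysis is to any one event, however it is misclassified. They do not measure how many events 11.4 would cause to be missed. The documents give no input for that.

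**The case against.** The case against has four parts.

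- **The word *only* is not in 11.4.** The section says when worsening should be reported and does not state that other worsening should not be. It also says all AEs must be recorded on a CRF, and section 11 is explicit and repeated. A site that follows section 11 will report. This stands, and it is why the fault is a contradictory instruction and not a rule that removes events. A single exception after a prohibition still invites the narrower reading.
- **TLR and amputation are discrete interventions, and the documents treat them as AEs.** The worked example in Protocol 8.3 and SAP 6.4 counts one amputation and two TLRs with no causality condition. Protocol 7.2 lists amputation and restenosis needing revascularisation as possible risks. This stands, and it makes loss of such an event much less likely than loss of worsening symptoms.
- **Other routes exist.** Events that lead to hospitalisation or a qualifying intervention are SAEs, and Table 12-1 sends SAEs to the sponsor within 10 working days without a causality test. The CEC adjudicates endpoint events whether related or not. Core laboratories read follow-up angiograms, and monitors check CRFs against source. These are real but partial guards. An SAE is defined as an AE that meets a seriousness criterion, so the AE question comes first, and monitors checking against two conflicting rules cannot tell which governs.
- **The SAP sentence on TLR says where the date comes from.** A reader might infer that an event without an AE is never counted. The text does not say so. It describes no other path, which is a gap and not an exclusion.

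A reader might also infer that the limb components are defined without regard to cause. That is not accurate for TLR, which requires attribution to the treated lesion.

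**Conclusion.** Wrong as written: the reporting rule contradicts itself. Section 11 requires any adverse change in a pre-existing condition to be recorded whatever its cause. Section 11.4 can be read as requiring it only when a study procedure is the cause.

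The probable consequence is under-recording of worsening limb ischaemia and wounds in the AE tables. The less probable one is delay or loss of a TLR, TVR or unplanned amputation on its way to the CEC. Both rest on the assumption that some sites follow 11.4 and not section 11, which the documents neither confirm nor exclude.

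It is tempting to go further and say that the clause threatens the primary safety result, because one event separates success from failure at 9 versus 10 MAEs in 112 subjects. The documents do not support that. The boundary applies to any single event, most MAE components are not worsening of the limb disease, and the two that are have other routes to detection. The size of any effect on the primary endpoint cannot be found from the documents.

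**What to change.** Reword the paragraph in Protocol 11.4 to match section 11: any worsening from baseline of a pre-existing condition or symptom after treatment has started is recorded as an AE whatever its cause. Relationship to the device stays in the separate field already collected under 11.4 and 11.5.3.

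Add to Protocol 12.2 that every repeat revascularisation and every amputation of the target limb is sent to the CEC whether or not the site filed an AE. Nothing is needed for deaths: 11.7 already puts all of them on the AE form, and 12.2 already has the CEC rule on them.

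The cost is about one sentence in each section and a reminder to sites. Expect a few more AE forms and possibly slightly less favourable observed rates.
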